#### Translational samples for research

*Tumor samples in MM subjects:* Bone marrow aspirates and a bone marrow biopsy will be collected at screening or Cycle 1 Day 1 (pre-dose) in subjects with MM. For subjects with MM, a bone marrow biopsy and bone marrow aspirations will be performed on-treatment (Cycle 3 Day 1). In subjects with MM a bone marrow biopsy and bone marrow aspirates will be performed at VGPR. A non-mandatory bone marrow biopsy and bone marrow aspirates can be performed at progression in MM subjects. If a standard of care (SOC) bone marrow will be performed, a bone marrow aspiration will be requested for research in MM subjects.

*Tumor samples in DLBCL subjects:* In subjects with DLBCL, archival tissue sample not older than 6 months will be collected. In DLBCL subjects with not enough archival tissue available, an optional fresh biopsy is recommended at screening or Cycle 1 Day 1 (pre-dose). An on-treatment biopsy (Cycle 3 Day 1) will be optional for subjects with DLBCL. An optional tumor biopsy will be taken in subjects with DLBCL at PR. A non-mandatory tumor biopsy can be performed at progression in DLBCL subjects. Biopsies in patients with DLBCL will be optional and a separate ICF will be provided.

*Blood samples for biomarker analyses in MM and DLBCL subjects:* Blood samples for exploratory analyses will be collected pre-dose at Cycle 1 Day 1, Cycle 1 Day 15, Cycle 2 Day 1, Cycle 3 Day 1 and after that every other cycle until Cycle 26 and then every 4 Cycles after Cycle 26, at progression, and at any response event.

*Blood samples, tissue samples and bone marrow aspirates for biomarker analyses in MM and DLBCL subjects:* In blood samples and tumor tissue/bone marrow aspirates/tumor cells DNA alterations such as mutations, copy number variation (CNV), and other DNA alterations will be assessed, RNA expression will be investigated in tumor tissue/bone marrow aspirates/tumor cells and/or blood samples (eg circulating tumor cells [CTCs] in the PBMC fraction/in PBMCs and/or the buffy coat) as well as protein expression and methylation status. Different assays such as next-generation sequencing (NGS), fluorescent-in situ hybridization (FISH), immunohistochemistry, and others will be performed to investigate translational research samples.

#### Assessment of Safety

In the Phase 1 safety portion, a Safety Review Committee (SRC) will monitor safety data on an ongoing basis. All dose escalation decisions will be made by the SRC upon review of all

available data. Determination of the MTD will be informed by all available data, including the overall tolerability of EZM0414.

#### Assessment of response

Assessment of response to treatment will be performed according to IMWG 2016 (Kumar, 2016; Appendix 1) consensus criteria in MM subjects and Lugano Classification (Cheson, 2014; Appendix 2) in DLBCL subjects.

**In MM:** IMWG 2016 consensus criteria that includes serum M-protein, 24-hour urine M-protein, serum free light chain kappa, lambda, and their ratio, bone marrow aspiration (complete response) and bone marrow biopsy (stringent complete response). Hence, subjects with MM would need to undergo a bone marrow biopsy or bone marrow aspiration for IMWG response assessment (Kumar, 2016; Appendix 1).

**In DLBCL:** International Working Group consensus response evaluation criteria in lymphoma, Lugano Classification (Cheson, 2014; Appendix 2). Hence subjects with a previously positive or unknown bone marrow biopsy at baseline would undergo a bone marrow biopsy in suspected CR.

#### **Part 2: Phase 1b Safety and Efficacy Dose Expansion**

In the dose expansion phase, Bayesian optimal phase 2 (BOP2) design will be used to evaluate safety and efficacy in subjects with or without select genetic translocation in R/R MM and R/R DLBCL.

In the dose expansion part, 60 subjects will be enrolled (20 subjects/cohorts) and treated:

- Cohort 1: R/R MM with t(4;14)
- Cohort 2: R/R MM without t(4;14)
- Cohort 3: R/R DLBCL

During the treatment period, subjects will receive EZM0414 in continuous 28-day cycles. EZM0414 will be administered orally once daily (QD) without food (nothing to eat two hours prior and one hour after EZM0414 dose, water is permitted as needed). The subjects who receive EZM0414 at MTD and do not have DLT in the dose escalation part of the study will be rolled over to a cohort of this dose expansion part, depending on their condition (R/R MM or R/R DLBCL) and the select genetic translocation for R/R MM. All subjects will continue to receive treatment at the MTD in Phase 1b part until disease progression, occurrence of unacceptable toxicity, or withdrawal of consent, or need for treatment prohibited on this study. Subjects with R/R MM regardless of t(4;14) status will be enrolled first. Dose modifications for EZM0414 are discussed in [Table 4](#).

Safety assessments will be performed throughout the study and at each study visit. Vital signs including blood pressure, heart rate, respiration rate, and temperature will be collected according to schedule of assessments ([Table 8](#) and [Table 10](#)).

A single 12-lead ECG will be collected at screening and triplicate ECGs, 1-minute apart will be collected at time points mentioned in [Table 8](#) and [Table 10](#).

Blood samples will be collected from all subjects for PK analyses at the time points mentioned in [Table 10](#).

At time points where vital signs, ECG and PK blood samples are required, the following order of collection is recommended 1) vital signs, 2) ECG and 3) blood sample for PK analyses and biomarker analyses.

#### Assessment of response

Assessment of response to treatment will be performed according to IMWG 2016 consensus criteria ([Kumar, 2016; Appendix 1](#)) in MM subjects and Lugano Classification ([Cheson, 2014; Appendix 2](#)) in DLBCL subjects. To assess response according to IMWG 2016, subjects with MM will undergo bone marrow aspirates or biopsies to assess CR or stringent CR, respectively. To assess complete response according to Lugano Classification, subjects with DLBCL might undergo a bone marrow biopsy. In MM subjects, treatment response will include serum M-protein, 24-hour urine M-protein, serum free light chain kappa, lambda, and their ratio. In DLBCL, imaging will be used to assess response.

#### Translational samples for research

*Tumor samples in MM subjects:* Bone marrow aspirates and a bone marrow biopsy will be collected from all MM subjects at baseline (at screening or Cycle 1 Day 1 pre-dose), on-treatment (Cycle 3 Day 1) and at VGPR. A non-mandatory bone marrow biopsy and bone marrow aspirates will be taken for subjects with MM at disease progression. If a SOC bone marrow will be performed, a bone marrow aspiration will be requested for research in subjects with MM.

*Tumor samples in DLBCL subjects:* In subjects with DLBCL, archival tissue sample not older than 6 months will be collected and if not available, an optional fresh biopsy will be performed at screening or Cycle 1 Day 1 (pre-dose). An optional on-treatment biopsy (Cycle 3 Day 1) and at PR will be performed in DLBCL subjects. Non-mandatory tumor biopsies in subjects with DLBCL will be taken at disease progression. All biopsies for subjects with DLBCL will be optional and a separate ICF will be provided.

*Blood samples for biomarker analyses in MM and DLBCL subjects:* Blood samples will be collected predose at Cycle 1 Day 1, Cycle 1 Day 15, Cycle 2 Day 1, Cycle 3 Day 1, after that at every other cycle until Cycle 26 and then every 4 cycles after Cycle 26, at progression, and at any response event.

*Blood samples, tissue samples and bone marrow aspirates for biomarker analyses in MM and DLBCL subjects:* In blood samples and tumor tissue/bone marrow aspirates/tumor cells DNA alterations such as mutations, copy number variation (CNV), and other DNA alterations will be assessed, RNA expression will be investigated in tumor tissue/bone marrow aspirates/tumor cells and/or blood samples (eg circulating tumor cells [CTCs] in the PBMC fraction/in PBMCs and/or the buffy coat) as well as protein expression and methylation status. Different assays such as next-generation sequencing (NGS), fluorescent-in situ hybridization (FISH), immunohistochemistry, and others will be performed to investigate translational research samples.

The translational research samples will be investigated for clones harboring t(4;14) translocation, somatic mutations such as SETD2, multiple myeloma SET domain (MMSET), expression of H3K36me2, and H3K36me3. Other markers and analysis might be performed as well.

Biomarker results including PD data will be correlated with PK data or outcome to investigate possible differences between subjects who respond to treatment versus those who do not respond.

## **7.2. Number of Subjects**

Phase 1 dose escalation: up to 36 subjects.

Phase 1b dose expansion: up to 60 subjects.

Total: approximately 96 subjects.

## **7.3. Treatment Assignment**

After obtaining written informed consent, subjects with R/R MM and R/R DLBCL will be screened according to the exclusion and inclusion criteria. Subjects who meet all selection criteria will receive a unique subject number upon enrollment in the study. Subject numbers will be allocated sequentially in the order in which subjects are enrolled. The Investigator or designee will enter the corresponding subject number in each subject's electronic case report form (eCRF).

In part 1, subjects will be administered EJM0414 based on the dose level they are enrolled in. Six dose levels starting at 100 mg, then 200 mg, 300 mg, 400 mg, 600 mg, and 900 mg as well as an optional step-down dose level of 75 mg (if needed) will be tested in this dose escalation part of the study.

In part 2, subjects will be enrolled and treated with EJM0414 at the MTD in 3 cohorts:

- Cohort 1: R/R MM with t(4;14)
- Cohort 2: R/R MM without t(4;14)
- Cohort 3: R/R DLBCL

All subjects in this study will receive EJM0414 as monotherapy orally once daily (QD) in 28-day cycles.

## **7.4. Duration of Treatment**

Subjects will be treated continuously until consent withdrawal, unacceptable toxicity, disease progression, or need for treatment prohibited on this study. Each treatment cycle will be of 28-day duration. There will be a 30-day safety follow-up.

## **7.5. Dose Adjustment Criteria**

### **7.5.1. Dose Limiting Toxicities**

Any adverse event (AE) which meets the criteria of a DLT as assessed by the Investigator and warrants action as per [Table 3](#), will be reviewed by the Safety Review Committee (SRC). No intra-patient dose reduction will be permitted in Cycle 1 of dose escalation. For subjects who require a dose interruption due to a DLT during cycle 1, the treatment will be restarted once the toxicity resolves to Grade  $\leq 1$  or baseline. However, an interruption in the administration of EJM0414, for more than 14 days will be discussed with the Sponsor's or Designee Medical

Monitor before treatment can be resumed. The DLT evaluable subjects will consist of dose escalation dose level subjects who received at least 80% of planned study treatment during cycle 1. If a subject is non evaluable, this subject will be replaced by a new subject.

Safety assessments will be performed throughout the study and at each visit. DLT period is 28 days of cycle 1 of the dose escalation part. AEs that are clearly and incontrovertibly due to the underlying disease or extraneous causes will not be considered as DLTs. All of the AEs of specified grades as listed in Table 3 will be classified as DLTs. Events will be assessed as DLTs according to the Common Terminology Criteria for Adverse Events (CTCAE 5.0), as shown in [Table 3 \(Appendix 5\)](#). When a subject is assessed to be experiencing a DLT, study treatment will be interrupted and DLTs will be managed by concomitant medication (as appropriate), treatment discontinuation, or a combination of these. All dose escalation decisions will be made by the SRC and Sponsor upon review of all available data. Determination of the MTD will be informed by all available data, including the overall tolerability of EZM0414.

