**Figure 4: Flowchart for Trial Conduct Using the BOPIN design**

$$* \text{DLT rate} = \frac{\text{Total number of patients who experienced DLT at the current dose}}{\text{Total number of evaluable patients treated at the current dose}}$$

A screening visit will occur within 28 days of signing an informed consent form (ICF). In Cycle 1 (except Day 2 and Day 3), EZM0414 will be administered orally once daily (QD) without food (no food two hours prior and one hour after EZM0414 dose, water is permitted without restrictions) in continuous 28-day cycles. Subjects will continue to receive treatment at the assigned dose level until disease progression, occurrence of unacceptable toxicity, withdrawal of consent, or need for treatment prohibited on this study. No intra-patient dose escalation will be permitted. DLT (as defined in [Table 3](#)) will be assessed during the first treatment cycle. Dose modifications for EZM0414 are discussed in [Table 4](#).

Safety assessments will be performed throughout the study and at each study visit. Vital signs including blood pressure, respiration rate, heart rate, and temperature will be collected according to schedule of assessments ([Table 8](#) and [Table 9](#)).

A single 12-lead ECG will be collected at screening and triplicate ECGs 1-minute apart will be collected at all other time points mentioned in [Table 8](#) and [Table 9](#). Subjects should be rested in a sitting position for 10 min prior to collection of all study ECGs.

Blood samples will be collected from all subjects for PK analyses at time points mentioned in [Table 9](#).

At time points where vital signs, ECG and PK blood samples are required, the following order of collection is recommended (1) vital signs, (2) ECG (3) Blood sample for PK analyses and biomarker analyses.

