**Table 3: Dose Limiting Toxicities**

Toxicity Category	Dose-Limiting Toxicity/CTCAE (version 5.0) Grade
Hematological toxicity	
 
Grade 4 neutropenia lasting more than 5 days
 
Grade 3 febrile neutropenia (ANC <math><1.0 \times 10^9/L</math> fever <math>\geq 38.4^{\circ}\text{C}</math> or <math>\geq 38^{\circ}\text{C}</math> for 1 hour)
 
Grade 3 thrombocytopenia with clinically significant bleeding
 
Grade 4 thrombocytopenia
 
Grade 4 Anemia unexplained by underlying disease
 

Other non-hematological toxicity	
 
Any other non-hematologic toxicity <math>\geq 3</math> except: 
 
Alopecia
 
Grade 3 nausea/vomiting or diarrhea for less than 3 days with adequate antiemetic and other supportive care
 
Grade 3 fatigue for less than one week
 
Grade 3 or higher isolated electrolyte abnormalities that last up to 3 days, are not clinically complicated, and resolve spontaneously, or respond to conventional medical interventions
 
Grade 3 or higher amylase or lipase elevation that is not associated with symptoms or clinical manifestations of pancreatitis
 
Grade 3 tumor lysis syndrome (TLS) that lasts up to 3 days, is not clinically complicated, and resolves spontaneously, or responds to conventional medical interventions.
 
 
 
Any patient meeting Hy's Law Criteria without alternate explanation, concurrent values of: 
 
ALT or AST elevation of <math>>3\times\text{ULN}</math>, and
 
TBL elevation of <math>>2\times\text{ULN}</math>, and
 
Absence of initial findings of cholestasis (ie, absence of elevation of ALP to <math>>2\times\text{ULN}</math>)
 
 
 

AE = adverse event; ALP = alkaline phosphatase; ALT = alanine aminotransferase; AST = aspartate aminotransferase; CTCAE = Common Terminology Criteria for Adverse Events; ECOG = Eastern Cooperative Oncology Group (ECOG); TBL = total bilirubin; ULN = upper limit of normal

*Note:* ALT is also referred to as serum glutamic pyruvic transaminase (SGPT); AST is also referred to as serum glutamic oxaloacetic transaminase (SGOT)

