**Table 4: Dose Modifications Instructions for Grade 1 – Grade 4 study drug-related Adverse Events\***

Toxicity a	During Therapy	Approximate Study Drug Dose Adjustment b
Excluding fatigue, alopecia, nausea, vomiting, or diarrhea not receiving adequate medical treatment. For management of QTcF prolongation please refer to Section 7.5.3, AST/ALT elevations please refer to Table 5, creatinine elevations please refer to Table 6, and INR elevations please refer to Table 7.		
Grade 1		
All occurrences	Continue study drug	Maintain dose level
Grade 2c		
Toxicity	During therapy	Approximate Study Drug Dose Adjustment b
1st occurrence	Monitor as clinically indicated	Maintain dose level
2nd occurrence	Interrupt study drug until resolved to Grade $\leq 1$ or baseline b	Maintain dose level
3rd occurrence	Discontinue study drug	Restart at one lower dose level
4th occurrence		Not applicable
Grade 3c,d		
Toxicity	During therapy	Approximate Study Drug Dose Adjustment b
1st occurrence	Interrupt study drug until resolved to Grade $\leq 1$ or baseline b	Restart at one lower dose level
2nd occurrence		Restart at second lower dose level
3rd occurrence	Discontinue study drug	Not applicable
Grade 4		
Any occurrence	Discontinue study drug	Not applicable

AST = aspartate aminotransferase; ALT = alanine aminotransferase; INR = international normalized ratio

\* Subjects diagnosed with a Covid-19 positive PCR test will be discontinued from treatment.

a The term occurrences applies to same AE term and not any AE term.b An interruption of any study drug for more than 14 days due to any toxicity must be discussed with the Sponsor's or Designee Medical Monitor before treatment can be resumed.c Excluding Grade 2 and 3 anemia: Subjects are allowed to continue study drug at their current dose level with transfusion per Investigator discretion.d Use of growth factors (G-CSF, GM-CSF) is permitted as per ASCO and ESMO guidelines

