For the purpose of overdose control, the current dose  $j$  and higher levels will be eliminated from further examination if  $\Pr(p_j > 0.25 \text{ data}) > 0.8$  and at least 3 subjects have been treated at the current dose level  $j$ , where  $p_j$  is the true DLT rate of dose level  $j$ ,  $j = 1, \dots, 6$ . This posterior probability is evaluated based on the beta-binomial model  $y_j | p_j \sim \text{binomial}(p_j)$  with  $p_j \sim \text{uniform}(0, 1)$ , where  $y_j$  is the number of subjects experienced DLT at dose level  $j$ . When the lowest dose is eliminated, stop the trial for safety. The probability cut-off 0.8 is chosen to be consistent with the common practice when the target DLT rate  $\leq 1/6$ , a dose with 2/3 subjects experienced DLT is eliminated. The above dose escalation/de-escalation and elimination rule can be equivalently presented in [Table 15](#), which will be used to conduct the trial.

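### DLT-evaluable requires 80% of Cycle 1 treatment with no exception for subjects who had a DLT, and the DLT rate mixes populations, so the same data can give opposite Table 15 actions

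*Protocol*

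**What the plan says.** **Who is evaluable.** Protocol Section 7.5.1: "The DLT evaluable subjects will consist of dose escalation dose level subjects who received at least 80% of planned study treatment during cycle 1". Protocol Section 14.3 and SAP Section 6.1.1 apply the same threshold within the Safety Population. Section 7.5.1 adds: "If a subject is non evaluable, this subject will be replaced by a new subject". None of these places makes an exception for a subject who had a DLT.

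**What a DLT does to dosing.** Section 7.5.1 requires treatment to be interrupted when a DLT is identified and allows discontinuation. Table 3 lists, among others, "Grade 4 thrombocytopenia" as a DLT. For any drug-related Grade 4 event, Table 4 says "Discontinue study drug". Section 7.5.1 also says that treatment restarts once a Cycle 1 DLT has resolved. That text and Table 4 must be reconciled.

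**How the rate is formed.**
- Figure 4: numerator "Total number of patients who experienced DLT at the current dose", denominator "Total number of evaluable patients treated at the current dose". SAP Figure 2 has the same formula.
- Table 15 and SAP Table 1: columns are evaluable patients, but the footnote defines the DLT count as subjects with one or more DLTs, without limiting it to evaluable subjects.
- Overdose-control rule in Section 14.1: elimination can apply once "at least 3 subjects have been treated at the current dose level". The Table 15 footnote says three evaluable subjects.
- Protocol Sections 14.6 and 14.6.1 and SAP Section 8.4.1: DLTs are evaluated on the DLT Population.

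**Oversight.** Section 7.5.1: "All dose escalation decisions will be made by the SRC and Sponsor upon review of all available data".

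**The concern.** The threshold exists to set aside subjects who had too little drug for the absence of a DLT to be informative. Applied without exception, it also removes subjects who had too little drug because they had a DLT. Such a subject is informative, and replacing that subject exchanges an observed event for a fresh observation.

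The documents then leave open how the excluded DLT counts. On the DLT Population it leaves both numerator and denominator, and the rate is biased downward. On the Figure 4 formula it stays in the numerator and leaves the denominator, and the rate is biased upward.

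The rate feeds escalation, de-escalation, elimination and the isotonic estimate of the MTD. Finding the MTD is part of the primary objective of Part 1, in a first-in-human study.

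**Working it through.** **1. The plan's own table.** The target rate is φ = 0.25. The documents do not give the two alternative rates behind the boundaries; I assume φ1 = 0.6φ = 0.15 and φ2 = 1.4φ = 0.35.

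- Escalation boundary: ln[(1−φ1)/(1−φ)] / ln[φ(1−φ1)/(φ1(1−φ))] = ln(0.85/0.75) / ln(0.2125/0.1125) = 0.1968 (plan: 0.197).
- De-escalation boundary: ln[(1−φ)/(1−φ2)] / ln[φ2(1−φ)/(φ(1−φ2))] = ln(0.75/0.65) / ln(0.2625/0.1625) = 0.2984 (plan: 0.298).
- Elimination: smallest y with Pr(p > 0.25) > 0.8 under Beta(1+y, 1+n−y), for n ≥ 3.

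All 27 cells of Table 15 are reproduced. The table is right; the problem is which subjects feed it.

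**2. When a DLT subject becomes non-evaluable.** In escalation, dosing is on Day 1 and Days 4–28 (Protocol Section 11), which is 26 doses. 0.8 × 26 = 20.8, so 21 are needed: 20/26 = 76.9% fails and 21/26 = 80.8% passes. Missing six or more doses fails. The 21st dose falls on Day 23, so stopping before it also fails. If all 28 days counted as planned, 0.8 × 28 = 22.4, so 23 would be needed, leaving room for only 26 − 23 = 3 missed doses.

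**3. Same data, three readings.**
- A: DLT Population for both counts.
- B: Figure 4 as written.
- C: any subject with a DLT is evaluable.

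| Data at one dose | A | B | C |
|---|---|---|---|
| 3 evaluable, 0 DLT; 1 DLT subject below 80% | 0/3 escalate | 1/3 de-escalate | 1/4 stay |
| 3 evaluable, 0 DLT; 2 DLT subjects below 80% | 0/3 escalate | 2/3 eliminate (posterior 0.949) | 2/5 eliminate (posterior 0.831) |
| 6 evaluable, 1 DLT; 1 DLT subject below 80% | 1/6 escalate | 2/6 de-escalate | 2/7 stay |
| 6 evaluable, 0 DLT; 1 DLT subject below 80% | 0/6 escalate | 1/6 escalate | 1/7 escalate |

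The posterior for 2/5 is 1 − BetaCDF(0.25; 3, 4) = 0.831, above the 0.8 cut-off. The last row shows that not every data set changes action.

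**4. Size of the bias.** Let f be the share of DLT subjects who fall below 80%. The documents give no value, so 25%, 50% and 75% are assumptions, as is the loss of no subjects without a DLT. The apparent rate is p(1−f)/(1−pf) under A and p/(1−pf) under B.

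| True rate p | Reading | f = 25% | f = 50% | f = 75% |
|---|---|---|---|---|
| 0.25 | A | 0.200 | 0.143 | 0.077 |
| 0.25 | B | 0.267 | 0.286 | 0.308 |
| 0.40 | A | 0.333 | 0.250 | 0.143 |
| 0.40 | B | 0.444 | 0.500 | 0.571 |

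At a true rate of 0.40, the chance that the first three evaluable subjects show no DLT, so that Table 15 says escalate, is 0.6³ = 0.216 if every DLT counts. Under A it is (1 − 0.333)³ = 0.296, (1 − 0.250)³ = 0.422 and (1 − 0.143)³ = 0.630.

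**The case against.** **One population is already named.** Section 14.6 puts DLT evaluation on the DLT Population, Table 15 is headed by evaluable patients, and its footnote can be read as merely counting subjects rather than events. Figure 4 taken literally could even exceed 1: four excluded DLT subjects over three evaluable ones is 4/3. Reading B may therefore not be what was meant, and the flowchart graphic itself could not be seen. This has force, but it leads to reading A, which is the least cautious of the three. Without B, the one-subject case is escalate against stay, and the two-subject case is still escalate against eliminate.

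**The bias depends on who is lost.** Subjects without a DLT can also fall short, for example through progression or withdrawal of consent. If a share g of them is lost, the rate under A is p(1−f)/[p(1−f) + (1−p)(1−g)], which equals p when g = f. So the downward bias requires DLT subjects to be lost more often. That is the likely direction, because a DLT itself triggers interruption, but its size is unknown.

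**The committee sees everything.** Each DLT goes to the Safety Review Committee, and decisions rest on all available data. An excluded DLT is not hidden, and the committee may well have acted on it. That softens the consequence but does not define the count entering Table 15 or the MTD estimate.

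**The study has stopped.** The SAP reports termination in mid-escalation on a business decision, with three dose levels conducted. TEAEs are listed without the 80% filter, and Protocol Section 14.6.1 leaves MTD determination to the CSR narrative. An amendment now changes no past escalation decision. But the SAP repeats the same definition for the DLT evaluation, and DLTs are among its primary endpoints.

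**Conclusion.** The concern holds. Followed as written, the definition removes subjects from the DLT evaluation because they had the event being counted, and the passages that form the rate conflict on whether that event is counted.

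The opposite actions in step 3 need no assumed toxicity rate. They need only that one or two DLT subjects at a dose fall below 80% and that Table 15 is applied as printed. For a related Grade 4 DLT before the Day 23 dose, Table 4 produces that shortfall by itself. The Day 23 cut-off takes 26 doses as planned; on 28, more subjects would be excluded.

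The rate series and the escalation probabilities are illustrative: they rest on assumed loss shares, no loss of subjects without a DLT and, for the probabilities, mechanical use of the table. At reporting, the effect is confined to the DLT evaluation for the three dose levels conducted. During conduct, the rule governed first-in-human escalation.

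**What to change.** In Protocol Sections 7.5.1 and 14.3 and SAP Section 6.1.1, define a DLT-evaluable subject as one who received at least one dose and either had a DLT in Cycle 1, or had none and received at least 80% of the planned Cycle 1 doses. State whether the skipped Days 2 and 3 count as planned. Replace only non-evaluable subjects who had no DLT.

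State in Figure 4, Table 15 and the elimination rule, and in SAP Figure 2 and Table 1, that numerator and denominator both use this population. The Section 7.5.1 restart text and the Table 4 Grade 4 row must also be reconciled; which one applies is a clinical decision outside this point.

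The cost is a few sentences in each document, with no extra subjects or data. Observed rates may move up or down, depending on which reading was in use. Because the study has ended, the working part of the change is the SAP definition and a CSR statement of how any DLT subject below 80% was counted at each dose level.
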